### **Study Population:**

All patients at risk for stroke or thromboembolism that demonstrated any degree of the significant leak on follow up TEE imaging at least 4-6 weeks following either epicardial, endocardial, or surgical LAAC were included in this study population. All patients were evaluated and followed with imaging, and per investigators' respective clinical judgement, then proceeded to have an intervention for leak closure with either detachable embolization coils, vascular plugs/CSO, or RFA.

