### **Primary Endpoints:**

1. To compare the efficacy of the three PDL closure modalities in patients with prior LAAC

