## **Sample Size:**

We will plan to aim for a total size of 160 patients in total among all three modalities.

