## **Statistical Analysis:**

Continuous variables will be summarized using mean and standard deviation, while categorical variables will be summarized as counts and percent of the total. Comparison analysis between groups will be made using Kruskal-Wallis tests for nonparametric data sets as appropriate. Leak sizes were measured initially and then via postprocedural follow-up, with overall rates of closure, minimal-mild leaks, and clinically significant leaks listed with associated p-values. All tests were two-tailed, and a  $P$  value less than 0.05 was considered statistically significant. All analyses were performed using SPSS Statistics version 28.0.0.0 (IBM).

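### The plan compares three closure modalities by p-value alone, with no between-modality difference or confidence interval, so a non-significant result could be read as similar efficacy when sizeable gaps cannot be excluded

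*Combined protocol and SAP*

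**What the plan says.** The Primary Endpoints section gives one item: "To compare the efficacy of the three PDL closure modalities in patients with prior LAAC". The Objectives section likewise sets out to compare the modalities on efficacy and safety.

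The Statistical Analysis section is the whole analysis plan. On this point it contains:

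- a summary rule: "categorical variables will be summarized as counts and percent of the total" (means and standard deviations for continuous variables);
- a between-group test: "Comparison analysis between groups will be made using Kruskal-Wallis tests for nonparametric data sets as appropriate";
- the output for leak closure: "with overall rates of closure, minimal-mild leaks, and clinically significant leaks listed with associated p-values". The same sentence describes leak size as measured at the start and again at follow-up;
- the criterion for a finding: "All tests were two-tailed", and a P "value less than 0.05 was considered statistically significant".

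On size, the Sample Size section says only "We will plan to aim for a total size of 160 patients in total among all three modalities". It gives no expected closure rate, target difference, precision or number per modality. The Study Population section says that patients, "per investigators' respective clinical judgement, then proceeded to have an intervention for leak closure", so arm sizes follow past practice.

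No section mentions a between-modality difference or ratio, a confidence interval or an equivalence margin.

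**The concern.** A comparative question needs an estimate of how far apart the modalities are and how precisely that is known. The planned output is a set of rates and a p-value. The one named between-group test, Kruskal-Wallis, is an omnibus test that yields a p-value and no effect estimate. A p-value above 0.05 does not distinguish modalities that close leaks about equally well from data too few to tell them apart.

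The Background justifies the study by the lack of any head-to-head comparison of these treatments. A bare statement of no significant difference could therefore be taken as evidence that coils, plugs or occluders and RFA are interchangeable. The same applies to the secondary endpoint: a modality with no complications would appear as 0%, with nothing to show how high the true rate might be.

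There is also an ambiguity. If the p-values attached to the closure rates compare initial with follow-up leaks within patients, the primary comparison of closure rates between modalities has no specified output at all.

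**Working it through.** **The plan's own figure.** The 160 cannot be reproduced, because no closure rate, difference, power or allocation is given. What can be checked is the precision that 160 patients would give under stated assumptions.

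**Inputs.** From the documents: 160 patients in total, three modalities, two-sided 0.05. Assumed: 160 evaluable patients; a near-equal split of 53/53/54 or, for imbalance, 90/50/20; a common observed closure rate p between 50% and 95%.

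**Half-width of the 95% interval for a pairwise difference.** h = 1.96 × √[p(1−p)(1/n₁ + 1/n₂)]

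For 53 v 53, √(2/53) = 0.1943. At p = 0.85, √(0.85 × 0.15) = 0.3571, so h = 1.96 × 0.3571 × 0.1943 = 0.136, or 13.6 points.

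| Closure rate | 53 v 53 | 90 v 20 | 50 v 20 |
|---|---|---|---|
| 95% | 8.3 | 10.6 | 11.3 |
| 90% | 11.4 | 14.5 | 15.6 |
| 85% | 13.6 | 17.3 | 18.5 |
| 80% | 15.2 | 19.4 | 20.7 |
| 70% | 17.4 | 22.2 | 23.8 |
| 50% | 19.0 | 24.2 | 25.9 |

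If the three intervals are Bonferroni-adjusted (0.05/3 each), the 53 v 53 figure at 85% rises from 13.6 to 16.6 points.

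**When observed rates differ without significance.** The table assumes equal observed rates. Otherwise the interval's far limit can lie well beyond these values. Take 45/53 (84.9%), 42/53 (79.2%) and 39/54 (72.2%):

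- 3×2 chi-square = 2.58 on 2 df, P = 0.27;
- largest gap: 84.9 − 72.2 = 12.7 points;
- Newcombe 95% CI: −3.0 to 27.7 points.

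A report confined to rates and a p-value would call this non-significant and leave a possible gap of nearly 28 points unstated.

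**Chance of missing a real gap.** By the two-sided normal approximation at 53 per arm, power for a true 15-point gap is 53% (90% v 75%), 46% (85% v 70%) and 41% (80% v 65%). Under these assumptions, a non-significant pairwise result despite a gap of that size is about as likely as not.

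**Zero complications.** The exact (Clopper-Pearson) 95% upper limit for 0/n is 1 − 0.025^(1/n). For n = 53 it is 6.7%; for n = 20 it is 16.8%.

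**The case against.** Five points can be made against the concern.

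- **Nothing says a non-significant P means equality.** This stands. A reader might infer that such a P will be treated as equal efficacy, or that P>0.05 is the likely outcome. The documents support neither. They contain no similarity rule and no expected rates. At 53/53/54, three-group chi-square power is about 81% for true rates of 90/80/65% but about 30% for 85/80/72%. The misreading could occur; it is not certain.
- **Any single figure for the gap is an assumption.** This stands. A reader might take 14 to 18 points as the imprecision at 160 patients, but that span comes from assuming 85% closure with either equal arms or a 90/50/20 split. The documents give neither the rate nor the split.
- **The wording is general.** The percent-of-total sentence covers all categorical variables, baseline ones included, and between-group comparison is promised elsewhere in the section. This is fair: that sentence does not show that closure will be pooled over modalities. But the promised comparison is still a test without an estimate.
- **Readers can compute intervals from counts.** This holds if counts are published by modality. It is no reason to leave the main result of a comparative study to the reader, and an adjusted difference cannot be recovered from counts.
- **Crude intervals may lend false authority.** Operators chose the treatment in a retrospective series, so a crude interval ignores confounding. This stands and shapes the fix: adjusted differences are needed beside the crude ones.

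**Conclusion.** The concern holds in a conditional form. The analysis plan provides no between-modality estimate or interval for a comparative primary aim, and it leaves open what the closure p-values compare. A non-significant result could therefore be read as similarity when sizeable gaps remain compatible with the data.

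How sizeable depends on closure rates and arm sizes that the documents do not state. With equal arms and equal observed rates, the half-width runs from about 8 points (95% closure) to 19 (50% closure). Against an assumed 20-patient arm it runs from about 11 to 26. When observed rates differ without reaching significance, the upper limit can be higher still, as in the worked example. The documents do not support going further, to say that the result will be non-significant or that it will be misread.

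This should be corrected before analysis, but it is a matter of estimation and reporting. It does not show that 160 patients is the wrong number.

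**What to change.** In the Statistical Analysis section:

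1. State that the closure p-values compare modalities, or name separately any p-value that compares initial with follow-up leaks.
2. Report closure as n/N with a 95% Wilson interval for each modality on its own denominator.
3. Report the three pairwise differences between modalities with 95% intervals, both crude (Newcombe) and adjusted for baseline variables already on the collection list, such as initial leak size and type of LAA closure. Name the adjustment method, and state whether the intervals allow for three comparisons.
4. Report complication rates by modality with exact 95% intervals, including zero counts.
5. Add that P≥0.05 will not be described as similar or equivalent efficacy or safety.

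If the Sample Size section is to state an expected precision, give a range together with the assumed closure rates and arm sizes. A single unconditional figure would carry an assumption the documents do not support.

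The cost is some plan wording, an adjusted model and a few more table columns; no extra patients or variables are needed. The intervals will be visibly wide. They express sampling error only: even the adjusted ones do not remove residual confounding from operator-chosen treatment, and the report should say so.

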### **1. Background**

Left Atrial Appendage (LAA) Closure (LAAC) is a potent technique of LAA isolation and exclusion for stroke prevention in patients with atrial fibrillation, with evidence from the PROTECT-AF and PREVAIL-AF trials, including their 5-year follow-up assessments, solidifying LAAC as a viable option in these patients with comparable stroke reduction in comparison to oral anticoagulation (OAC) as well as a reduction in bleeding risk, hemorrhagic CVA, and mortality [1-3]. However, the surge in the multiple methods of LAA exclusion has also brought to attention postprocedural complications specific to LAAC, namely, peri-device leaks (PDL) [4]. The stroke implication and classification of PDL itself still lacks consensus, with an increased thromboembolic (TE) potential due to PDL seen in patients with LARIAT and surgical ligation procedures, yet no statistically significant relationship seen in percutaneous and endocardial LAA closure approaches [5-9]. PDL > 5mm has been widely accepted as clinically significant, although there remains limited data with no current established guidelines. [5, 6, 10]. Placement of a septal occluder device such as Amplatzer Vascular Plug, Detachable embolization coils, Gore Cardioform Septal Occluder (CSO; W.L. Gore and Associates, Newark DE), and radiofrequency ablation (RFA) have all emerged as options to resolve residual PDL and post-surgical/ligation leaks [5, 10-12]. However, there exists no head-to-head comparison between these modalities. Given their emergence, we proposed a multi-center observational study to further assess and evaluate these three treatment modalities for their efficacy for leak closure, assessment of pre-, peri- and post-procedural characteristics after leak closure, TE events, and bleeding risk, and complication rates.

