## **Data/Variable Points for Collection:**

- Age
- Sex
- Height
- Weight
- BMI
- Diabetes (y/n)
- Smoking (y/n)
- Dyslipidemia (y/n)
- Prior stroke/TIA (y/n)

- Prior deep venous thrombosis/pulmonary embolism (y/n)
- Ejection Fraction
- History of CAD (y/n)
- Congestive heart failure (y/n)
- Chronic Kidney Disease (y/n)
- Type of Atrial Fibrillation (paroxysmal, persistent, permanent)
- Baseline antithrombotic regimen (aspirin, clopidogrel/prasugrel/ticagrelor, warfarin, direct oral anticoagulant, heparin)
- TIA/stroke after Watchman
- History of major bleeding
- High Fall risk (y/n)
- Previous major bleeding (y/n)
- Previous minor bleeding (y/n)
- Thromboembolism while on oral anticoagulant
- CHA2DS2-VASc Score
- HAS-BLED Score
- Time passed since LAA closure (months)
- Type of LAA Closure (watchman/watchman FLX, amulet, lariat, surgical ligation, atriclip)
- Device Size (if applicable)
- Thrombus on device (y/n)
- Peri-device/central leak size in mm
- Acute success (end of procedure closure) (y/n)
- Procedure duration (minutes)
- Flourosopy time (minutes)
- Contrast usage (mL)
- Hospital length of stay
- Type of procedural anesthesia (general vs light sedation vs local)
- Procedural imaging (TEE, ICE, or both)
- Devices attempted
- Devices deployed
- Combination procedures (combined AF ablation, or LAA occlusion + AF ablation)
- Size/number of devices (plugs/coils)
- Major procedural complications from postoperative day 0-7: stroke, TIA, air embolism, myocardial infarction, cardiac tamponade, device embolization, ventricular tachycardia
- Minor procedural complications from postoperative day 0-7: pericardial effusion
- Complications seen within 90 days of the procedure: cardiovascular death, non-cardiovascular death, stroke/TIA, pericarditis
- Follow-up transesophageal echocardiogram time (months)
- Size of leak at follow up (in mm)
- Follow-up time
- Follow up antithrombotic regimen

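### Efficacy p-values are attached, unadjusted, to three leak-band rates with no primary one named, and the minimal-mild p-value cannot be read as better or worse

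*Combined protocol and SAP*

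**What the plan says.** All references are to the combined protocol and SAP.

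- **Primary Endpoints** lists one item, a comparison of the efficacy of the three modalities. It names no variable.
- **Data/Variable Points for Collection** records leak size as a measurement, both at baseline ("Peri-device/central leak size in mm") and afterwards ("Size of leak at follow up (in mm").
- **Statistical Analysis** names Kruskal-Wallis for between-group comparison, as appropriate, without listing the variables it covers. The sentence on leak outcomes then has results reported "with overall rates of closure, minimal-mild leaks, and clinically significant leaks listed with associated p-values". It gives no mm limits for the bands, no test for the rates, no primary band and no multiplicity rule.
- The same section sets the threshold for every test: "All tests were two-tailed", and a P "value less than 0.05 was considered statistically significant".
- **Sample Size**: "We will plan to aim for a total size of 160 patients in total among all three modalities".
- **Background** has the only cut-point: "PDL > 5mm has been widely accepted as clinically significant, although there remains limited data with no current established guidelines".

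**The concern.** Because efficacy has no defined variable, the leak-outcome sentence is the only indication of how the primary endpoint will be tested. As written, it yields three p-values on three rates that together describe one ordered outcome. Three problems follow.

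1. The middle rate does not measure efficacy. A better modality moves patients from significant to mild and from mild to closed, so the share in the middle can rise, fall or stay put.
2. With three p-values and none designated primary, any one of them could be reported as the efficacy result.
3. Testing the rates one at a time ignores their order and any size differences within a band. With about 160 patients over three groups, that may cost power.

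**Working it through.** **Inputs from the plan.** Total 160; two-sided 0.05 for each test; leak size in mm; p-values on three band rates. The 160 cannot be reproduced, because the plan gives no effect size, rates, SD, power or allocation.

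**Assumptions.** Groups of 54/53/53. The plan states no split; modality was chosen "per investigators' respective clinical judgement, then proceeded to have an intervention for leak closure". A share of leaks is closed (0 mm) and the rest follow a gamma distribution with shape 3. Clinically significant means above 5 mm, taken from the Background. Band rates are tested by chi-square. Each scenario has 3,000 simulated trials, so the Monte Carlo standard error is at most √(0.5 × 0.5 / 3000) = 0.9 points.

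**Step 1: direction of the middle rate.** With C the closure rate and S the significant-leak rate, the minimal-mild rate is M = 1 − C − S, so ΔM = −ΔC − ΔS. A better modality has ΔC > 0 and ΔS < 0, so the sign of ΔM is undetermined. This needs no assumed effect size. As an illustration, take closure 40/30/20% and significant leak 3/12/26%. Then M is 100 − 40 − 3 = 57%, 100 − 30 − 12 = 58% and 100 − 20 − 26 = 54%. The modalities differ clearly, yet M barely moves.

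**Step 2: false positives.** Three independent tests at 0.05 would give 1 − 0.95³ = 14.3%. The three band rates sum to one and are therefore dependent. Simulated with no difference between modalities, at least one is significant in 11.6% of trials (60% closed) and 12.1% (30% closed).

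**Step 3: power (%).** In A, B, D and E the mean residual leak is 2.5/3.5/4.5 mm; in C it is equal across groups.

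| Closure in the three groups | Closure rate | Minimal-mild rate | Significant rate | Three rates, Bonferroni | Unordered 3×3 | Kruskal-Wallis, bands | Kruskal-Wallis, mm |
|---|---|---|---|---|---|---|---|
| A. 40/30/20% | 51 | 6 | 91 | 85 | 89 | 88 | 97 |
| B. 70/60/50% | 46 | 7 | 71 | 63 | 68 | 60 | 71 |
| C. 90/80/70% | 63 | 56 | 6 | 48 | 49 | 63 | 62 |
| D. 60% in all | 4 | 16 | 47 | 32 | 38 | 7 | 11 |
| E. 30% in all | 5 | 39 | 78 | 67 | 68 | 19 | 51 |

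Repeat runs move these figures by a few points. A 3 mm cut and a 100/40/20 split were also tried. The advantage over the Bonferroni and 3×3 analyses in B is not robust to them: with 100/40/20 and a 5 mm cut, mm has 62% against 68% and 71%.

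**Step 4: order or mm?** The source of the gain depends on the model. If one modality is simply shifted 2 mm worse (normal latent leak, SD 3 mm, floored at 0, closure 44/44/20%), power is 80.3% for the unordered 3×3 test, 88.3% for Kruskal-Wallis on bands and 92.9% on mm. Order adds 88.3 − 80.3 = 8.0 points and mm a further 92.9 − 88.3 = 4.6. In C the gain over the 3×3 test is all from order. In A it is all from mm.

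**The case against.** The strongest reply is that the power argument depends on what is assumed, and that stands. A reader might infer that cutting mm into bands generally costs power. The documents do not support this, because they give neither closure rates nor residual sizes. In C the rank test on mm only matches the closure rate (62% against 63%). In D and E it is well below the significant-leak rate (11% against 47%, and 51% against 78%).

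A reader might also infer that the plan rules out an analysis of mm. It does not. Kruskal-Wallis is the one between-group test named, and nothing excludes applying it to leak size. The text is ambiguous: it never says that mm will be tested, and the p-values it mentions for leak outcomes belong to rates.

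Nor are the bands without clinical meaning. The Background says there is no guideline but also calls leaks above 5 mm widely accepted as clinically significant. That is a good reason to keep a test of that rate rather than reduce it to description.

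None of this rescues the minimal-mild p-value, or three unadjusted p-values with no primary one.

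**Conclusion.** The point holds in a limited form. Two parts are firm. The minimal-mild p-value has no direction of benefit, which follows from arithmetic alone. Three unadjusted tests with no primary one carry about an 11 to 12% chance of at least one false-positive efficacy result; that figure assumes chi-square tests and the simulated leak distributions.

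The power loss is conditional. With equal groups and a 5 mm cut, one test on mm gains over both error-controlled band analyses when a better modality closes more leaks: 97% against 85% and 89% in A, and 62% against 48% and 49% in C. Against the best single rate the gain can be nil, and it turns into a clear loss when modalities differ only in the size of unclosed leaks. All closure rates, residual sizes, group splits and band limits behind these figures are assumed. This is a cheap, worthwhile improvement, not a fault that invalidates the comparison.

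**What to change.** In Statistical Analysis:

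1. Make the primary efficacy comparison one tie-corrected Kruskal-Wallis test, the method already named, on follow-up leak size in mm, with complete closure scored 0.
2. Delete the p-value on the minimal-mild rate and report that band as count and percent.
3. Keep the closure rate and the clinically significant leak rate as named secondary comparisons, with their p-values labelled as secondary. State the mm limit that defines a significant leak, since the test depends on it.

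The cost is two or three sentences. The data are already on the collection list and the primary test is already in the plan. There are two downsides. A rank-based effect is less familiar than a closure rate, so the rates should stay in the table. The rank test also has little power if modalities differ only in residual size among unclosed leaks and many leaks close, which is why the significant-leak rate remains a secondary test. The change does not address confounding from modality being chosen by clinical judgement.

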## **2. Objectives:**

### Primary Objective:

Our main objective is to collect data from multiple different centers that use different modalities to currently treat either central or peri-device leaks that occur after incomplete LAA closure, and compare each modality in their efficacy and safety outcomes.

Primary Outcome: To compare the efficacy of the three current methods of PDL closure modalities in patients with prior incomplete LAAC.

Secondary Outcome: To compare the rates or reduction of rates of thromboembolic events and procedure-related complications in patients after successful PDL closure with any of the three closure modalities.

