## **3. Research Methods and Statistical Considerations:**

### **Research Methods:**

This will be a multi- center retrospective observational comparison study.

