## **Data storage/Confidentiality:**

Data will be collected in word documents, PDFs, and excel sheets. Data recorded on the worksheets will be entered into a secure password protected computer database by the research staff at corresponding heart institutes/cardiac centers. Only investigators involved in the study will have access to the data. All data will be reported in aggregate form and no names will be used for any publications resulting from the research. De identification of data will be done at the earliest.

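### The closure comparison pools centres with no centre term and no listed centre field, so if modality clusters by centre a P<0.05 can reflect centres rather than modalities

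*Combined protocol and SAP*

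**What the plan says.** Under Research Methods the design is given as: "This will be a multi- center retrospective observational comparison study". The Primary Objective is to "collect data from multiple different centers that use different modalities to currently treat either central or peri-device leaks" and to compare the modalities. Under Study Population, patients were followed and then, according to investigators' "respective clinical judgement, then proceeded to have an intervention for leak closure with either detachable embolization coils, vascular plugs/CSO, or RFA". The Inclusion Criteria add that the operator's judgement governed who was treated, without fixed limits on leak size or on time since the original closure.

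The only sample size statement is: "We will plan to aim for a total size of 160 patients in total among all three modalities". No number is given per modality or per centre, and the number of centres is not stated.

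The Statistical Analysis section has two elements that compare groups. The first is: "Comparison analysis between groups will be made using Kruskal-Wallis tests for nonparametric data sets as appropriate". The second is leak results shown as "overall rates of closure, minimal-mild leaks, and clinically significant leaks listed with associated p-values". A P "value less than 0.05 was considered statistically significant". The section has no stratification, regression, random effect or cluster-robust variance, and it does not mention centre. The section on data points for collection runs from age to the follow-up antithrombotic regimen and lists no centre, site or operator. The Data storage/Confidentiality section does say that data are entered "by the research staff at corresponding heart institutes/cardiac centers".

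**The concern.** The primary endpoint is a comparison of efficacy between three modalities that were chosen in practice, not allocated. The protocol's own description makes it plausible that the choice depended partly on where the patient was treated. Operator-led case selection gives a reason for closure rates to differ between centres as well. When both are true, patients in one modality group share centres, their outcomes are correlated, and a test that treats all 160 as independent has too small a variance. A difference between centres can then appear as a difference between modalities.

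The Background section says that no head-to-head comparison of these modalities exists, so readers may lean on this result. Under the plan as written they would see an unadjusted p-value. They would have no table showing how modality was spread over centres and no within-centre comparison to set beside it.

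**Working it through.** **The plan's own figure.** The total of 160 cannot be reproduced, because the documents give no closure rate, effect size, power or allocation. It is taken as given.

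**Inputs.** From the documents: N = 160, three modalities, two-sided 0.05, no centre term. Assumed, because the documents are silent: number of centres k (equal size), ICC of closure within centre, overall closure rate, and s, the share of each centre's patients who receive its main modality. The remainder is split evenly over the other two modalities, and main modalities are spread evenly over centres. No test is named for the rates, so Pearson's chi-square on the 3x2 table is assumed. For a yes/no outcome the Kruskal-Wallis statistic equals Pearson's multiplied by (N - 1)/N = 159/160, so the choice between them hardly matters.

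**Formula.** The association of modality with centre is r = ((3s - 1)/2)^2, which is 0 at s = 1/3 and 1 at s = 1. The variance inflation is DE = 1 + (160/k - 1) x ICC x r. The type I error is P(chi-square on 2 df > 5.99/DE), which equals exp(-5.99/(2 x DE)).

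**Numbers put in, 12 centres and ICC 0.05.** (160/12 - 1) x 0.05 = 12.33 x 0.05 = 0.617. The simulation column has no true modality difference, 75% closure, beta-binomial centre rates and 100,000 replicates.

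| Main-modality share s | r | DE | Type I error, formula | Type I error, simulation |
|---|---|---|---|---|
| 1/3 (unrelated) | 0 | 1.000 | 5.0% | 5.0% |
| 50% | 0.0625 | 1.039 | 5.6% | 5.6% |
| 70% | 0.3025 | 1.187 | 8.0% | 7.9% |
| 80% | 0.49 | 1.302 | 10.0% | 10.1% |
| 100% (one per centre) | 1 | 1.617 | 15.7% | 15.9% |

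Smaller repeat simulations of the same setting gave about 10-11% at 80%.

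**Range.** Over 6-18 centres, ICC 0.02-0.10 and closure 75-80%, the simulated error is about 5% (unrelated), 5-8% (50% share), 6-19% (70%), 6-28% (80%) and 8-45% (one modality per centre). With ICC = 0, DE = 1 whatever the share, and the error stays at about 5%. With 12 uneven centres of 6-37 patients and ICC 0.05, the five figures are 4.8%, 5.8%, 8.6%, 11.8% and 19.4%.

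**The stratified alternative.** The centre-stratified generalised Cochran-Mantel-Haenszel (CMH) test on 2 df held 4.7-4.9% in the 12-centre cells with a share below 100%, and 4.3-5.3% in every equal-centre cell with ICC above 0 and share below 100%. At a 100% share it has nothing to compare within centres.

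**What it costs in power.** Take 12 equal centres, ICC 0.05 and assumed true closure of 70/80/90%. The unadjusted test has about 62% power. The stratified test has about 43% at a 70% share, 31% at 80% and 19% at 90%. The unadjusted figure is partly flattered by its inflated error, but the loss is similar where that test is valid: at ICC 0 and an 80% share, 64% against 33%.

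**The case against.** The strongest reply is that the premise is not established. The Primary Objective's phrase about centres fits a group of hospitals that each use several modalities as well as it fits hospitals with one each, and investigator judgement may concern whether to close a leak as much as how. At a 50% share the inflation is under one percentage point in the 12-centre setting. This stands: the figures illustrate a risk and do not measure this study. A reader might infer that each centre used a single modality and that the comparison is therefore wholly confounded with centre. The documents do not say so.

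A second reply concerns the data list. It also lacks an explicit modality field, a patient identifier and a procedure date, so it may be only a list of clinical variables, and the entering site would reveal the centre. This also stands. It cannot be concluded that centre is unknown, only that the plan neither secures it nor uses it.

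A third reply is that stratification is costly and limited. It can halve power in a study of 160 and is weakest where clustering is strongest. It also leaves patient-level confounding within centres untouched, and it needs a binary closure endpoint that the documents, which speak of efficacy, do not define. A reader might infer that the stratified test must become the primary analysis. These points count against that, and numerical cut-offs for abandoning it would be arbitrary. They do not count against reporting it beside the unadjusted result.

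Finally, parts of the document are in the past tense, so de-identification and analysis may already have happened. In that case the stratified result should be labelled as added afterwards. The table and the limit on the conclusion remain useful, although restoring a centre code might then take more work.

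**Conclusion.** The point holds in conditional form. The plan compares modalities pooled over centres, has no centre term, and lists no centre field. If modality is associated with centre and closure differs between centres, a significant unadjusted p-value can reflect centres. Under the assumed 12 equal centres, ICC 0.05 and 75% closure, the true error behind a nominal 5% is about 5% with no association, 8% at a 70% main-modality share, 10-11% at 80% and about 16% in the extreme of one modality per centre. Fewer centres or a larger ICC raise these figures, and an ICC of 0 removes the inflation.

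The documents support neither a claim that the inflation is present nor a claim about its size. What they do show is that the plan as written gives the reader no means of telling which case applies. That is more than missing detail, because it limits what the primary comparison can be said to mean.

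**What to change.** 1. Keep a coded centre identifier in the analysis dataset and add it to the list of data points. It need not identify patients.
2. Report a table of modality by centre.
3. Define closure as a yes/no outcome for this purpose. Report a centre-stratified comparison (for example the generalised CMH test) beside the unadjusted one, as a stated sensitivity analysis. Give the number of centres and patients that contribute to it, since centres with a single modality do not.
4. Attribute a difference to modality only if the within-centre estimates agree with the unadjusted ones in direction and size. Non-significance of the stratified test alone should not be read as disagreement, given its lower power.
5. If few or no centres used more than one modality, report the comparison as descriptive and state that centre and modality effects cannot be separated.

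This is a cheap improvement: one coded column, one table, one further analysis and a few sentences in the plan, using information the centres should already hold. The downside is a little more analysis and a stratified result that is less precise (about 43% against 62% power at a 70% share, and 31% against 62% at 80%, under the assumptions above). That is why it should not be made the sole primary test. It does not remove confounding by patient characteristics within centres, which needs separate treatment.
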